11.0 Data Management* and Confidentiality

We will present descriptive statistics on the proportion of people screened who were eligible and ineligible, and the number randomized. We will describe the health characteristics and self-reported adherence of the completers and non-completers based on the available data.

We will construct linear mixed models to examine within-person changes in levels of estradiol, testosterone, DHEAS, and SHBG from grape juice to white wine, including a random subject intercept and fixed effects for treatment and sequence. We will assess the potential for a carryover effect by evaluating a cross-product term for treatment and sequence. We will use a logarithmic transformation for skewed distributions of the sex hormone levels.

We will use Markov Chain Monte Carlo (MCMC) multiple imputation. For each treatment arm, we will use the SAS “proc mi” procedure to generate 10 multiply imputed datasets that incorporate appropriate variability across the imputations. We will use the SAS “proc mianalyze” procedure to combine the results from the imputed data sets to properly reflect the uncertainty due to missing values.

Our primary analysis will use an intention-to-treat (ITT) approach, classifying participants according to their assigned treatment arms regardless of adherence to study protocol. In a sensitivity analysis, we will use a per-protocol approach in which a participant’s follow-up will be terminated at the time, if any, at which they cease to follow the protocol, and we will adjust for pre-randomization and post-randomization factors that may predict adherence.

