Our primary endpoint is free estradiol (estradiol divided by SHBG). We should have excellent power to assess effects of alcohol on DHEAS but reasonable power to detect effects on estrone sulfate, although, as a pilot study with an intentional goal of training and career development, power is but one dimension on which to evaluate the merits of the trial. We have used standard formulae to estimate the minimum detectable difference for 2-period crossover trials (http://hedwig.mgh.harvard.edu/sample_size/js/js_crossover_quant.html). Using the 4-week results of a similar crossover trial of alcohol on changes in estrone sulfate and DHEAS, and using the dosage of 15 gm/day that most closely approximates the dosage proposed in this application, we can estimate the proportional changes anticipated with varying degrees of power, as shown below at a two-sided 0.05 significance level. Based upon data presented in that trial, we estimate the SD of within-person differences to be 42% for estrone sulfate and 13% for DHEAS.

Power	Minimum Detectable Difference	
	Estrone sulfate (ng/dl)	DHEAS (ng/dl)
50%	19%	6%
80%	28%	9%
90%	32%	10%

For comparison, the increases in estrone sulfate in previous trials of alcohol were 15-21% in a trial of premenopausal women and 7-22% in a trial of postmenopausal women.

The comparable effects on DHEAS were 4-7% and 5-9%. Thus, we appear to have adequate power to detect effects of the expected size from previous crossover trials. Moreover, we have particularly strong power to exclude virtually all clinically significant increases (e.g., increases of 10% or larger) in DHEAS.

Our results would also provide all necessary information to power a more definitive trial of estrone and other estrogens.

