23.0 Local Number of Subjects

We will screen and enroll participants until we have 20 participants who have completed the ten weeks of the study.

BIDMC follows over 5,000 women with breast cancer who account for over 8,000 visits yearly, of whom over 3,500 are likely to be ER+ and hence potentially eligible for our trial.

We plan to contact as many as 100 participants to ensure that at least 20 women complete the study. This pilot study is funded by very limited project funds from

[name] K01 award and comprises 20 women – a small enough total to be readily completed at a single center.

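### Imputed results are pooled with no complete-data degrees of freedom given; unless they are supplied, intervals for about 20 women come out about 8% narrower than small-sample ones

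*Combined protocol and SAP*

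**What the plan says.** The analysis plan is in section 11.0 of the combined protocol and SAP. For the hormone comparisons it states: "We will construct linear mixed models", "including a random subject intercept and fixed effects for treatment and sequence". For missing values, PROC MI is to be run by treatment arm to "generate 10 multiply imputed datasets that incorporate appropriate variability across the imputations", and PROC MIANALYZE is the "procedure to combine the results from the imputed data sets to properly reflect the uncertainty due to missing values". No option of either procedure is named. The section gives no complete-data degrees of freedom, no small-sample pooling rule, no denominator degrees-of-freedom method for the mixed model and no expected amount of missing data.

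On size, section 23.0 says: "We will screen and enroll participants until we have 20 participants who have completed the ten weeks of the study". The primary analysis is by intention to treat, so women who drop out may be analysed in addition to the 20 completers; their number is not given. The power paragraph of section 11.0 works "as shown below at a two-sided 0.05 significance level".

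**The concern.** A mixed model fitted to 20 women in two periods carries about 18 to 19 degrees of freedom for the treatment effect: 19 for the model as written, 18 once the treatment-by-sequence term is added. Pooling does not inherit that figure. The standard combining rule computes degrees of freedom from the number of imputations and the share of variance due to missing data, and sample size does not enter. The less is missing, the larger the result, so a trial of 20 women can be judged against an almost normal critical value.

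Interval width matters here. Section 1.0 hypothesises that the expected hormone increases will not be seen, and section 11.0 claims strong power to exclude DHEAS increases of 10% or more. Exclusion rests on the upper confidence limit, and an interval that is too narrow places that limit too low.

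**Working it through.** **Inputs from the documents.** 20 completers (section 23.0); two-sided 0.05 and m = 10 imputations (section 11.0); and, also in section 11.0, "we estimate the SD of within-person differences to be 42% for estrone sulfate and 13% for DHEAS".

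**Assumed.** The relative variance increase from missing data, r, is taken as 0.02 to 0.2. The documents give no basis for a value.

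**Step 1: reproduce the plan's own power table.** The standard error is SD/√20: 42/4.472 = 9.39 for estrone sulfate and 13/4.472 = 2.91 for DHEAS. The table below gives minimum detectable differences (estrone sulfate/DHEAS, %). The t columns solve the noncentral t equation; the normal column is (1.96 + z for power) × SE.

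| Power | Plan | t, 18 df | t, 19 df | Normal |
|---|---|---|---|---|
| 50% | 19/6 | 19.5/6.0 | 19.4/6.0 | 18.4/5.7 |
| 80% | 28/9 | 27.8/8.6 | 27.7/8.6 | 26.3/8.1 |
| 90% | 32/10 | 32.2/10.0 | 32.1/9.9 | 30.4/9.4 |

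The plan's figures agree with t quantiles on 18 to 19 df to within rounding. They do not fit the normal approximation. The design stage therefore already allowed for the small sample.

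**Step 2: degrees of freedom in pooling.**
- Standard rule: df = (m − 1)(1 + 1/r)².
- Barnard-Rubin rule: 1/(1/df + 1/df_obs), where df_obs = [(ν + 1)/(ν + 3)] × ν × (1 − λ), λ = r/(1 + r), and ν is the complete-data df.

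Example with ν = 18 and r = 0.1:
- Standard: 9 × 11² = 1,089.
- λ = 0.1/1.1 = 0.091, and df_obs = (19/21) × 18 × 0.909 = 14.8.
- Barnard-Rubin: 1/(1/1,089 + 1/14.8) = 14.6.

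In the next table, narrowing is 1 − (standard critical value)/(Barnard-Rubin critical value), from unrounded values. Size is the probability that a t variable on the Barnard-Rubin df exceeds the standard critical value in either direction.

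| r | Standard df | Critical value | Barnard-Rubin df | Critical value | Narrower by | Size by formula |
|---|---|---|---|---|---|---|
| 0.02 | 23,409 | 1.960 | 16.0 | 2.120 | 7.6% | 6.8% |
| 0.1 | 1,089 | 1.962 | 14.6 | 2.136 | 8.2% | 6.9% |
| 0.2 | 324 | 1.967 | 13.0 | 2.160 | 8.9% | 7.1% |

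With ν = 19 the narrowing is 7.1 to 8.4%. If 25 women are analysed (ν = 23), it is about 6 to 7%.

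**Step 3: actual size by simulation.** The size column treats the pooled statistic as exactly t-distributed, so the whole procedure was also simulated under no effect. Settings: 20 women, 1 to 4 second values missing at random, normal data, within-person correlation 0.5 to 0.8, and a paired mean difference in place of the mixed model.
- Two periods imputed jointly by a simple model, infinite-df pooling: about 6.0 to 6.5%.
- The same with extra covariates in the imputation model: about 5.2 to 6.2%.
- Arms imputed separately: about 2.4 to 6.8%, depending on how much is missing and how strongly the periods correlate.
- Simple joint imputation with the Barnard-Rubin rule: about 4.2 to 4.9%.

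**The case against.** Three points on the other side have force.

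First, a reader might infer that the plan prescribes the infinite-df default. It does not. Section 11.0 names the procedure and no options, and Step 1 suggests that the team does think in small-sample terms. The gap is an unspecified input, not a stated error. It is still more than missing detail, because running the named procedure with nothing further supplied produces the near-normal critical value.

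Second, a reader might infer that the 5% test really runs near 7%, or that every hormone result would be too optimistic. Neither is supported. The figure near 7% is the formula value only. In small samples the imputation variance tends to be conservative and partly offsets the liberal critical value. Section 11.0 also says that imputation is done by treatment arm. Read literally, this cuts the link between a woman's two values, inflates the variance and can bring the error to or below 5%. So the direction of any error in test size depends on how that phrase is carried out.

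Third, the practical effect is modest in a pilot. At r = 0.1, using the plan's SDs and leaving out the inflation of the standard error from missing data, the half-width goes from 1.962 × 2.91 = 5.7 to 2.136 × 2.91 = 6.2 percentage points for DHEAS. For estrone sulfate it goes from 1.962 × 9.39 = 18.4 to 2.136 × 9.39 = 20.1. On those figures the 10% DHEAS exclusion would change only for an estimated increase between about 10 − 6.2 = 3.8% and 10 − 5.7 = 4.3%.

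These points limit the claim about error rates. They leave the interval comparison standing.

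**Conclusion.** The point holds as an omission with a predictable effect. If complete-data degrees of freedom are not supplied, pooled intervals for 20 women are 7.6 to 8.9% narrower than the Barnard-Rubin intervals. That rests on complete-data df of 18 and an assumed r of 0.02 to 0.2. The gap shrinks to about 6 to 7% if the intention-to-treat set reaches about 25 women. No single figure for the true test size can be defended, because it depends on the amount of missing data and on the imputation model, and the documents settle neither. The pooling step should meet the same small-sample standard as the plan's own power table. Nothing here shows that multiple imputation is the wrong primary approach; replacing it with a likelihood analysis would be a separate trade-off.

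**What to change.** Add one or two sentences to section 11.0:
- Name the mixed model's denominator degrees-of-freedom method, for example Kenward-Roger.
- State that PROC MIANALYZE will be given the complete-data degrees of freedom through its EDF option, so that the Barnard-Rubin rule applies. The value is about 18 for 20 women, and correspondingly larger if more women are in the intention-to-treat set (about 23 for 25).

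The cost is one software option and slightly wider intervals: 1/(1 − 0.076) to 1/(1 − 0.089), or about 8 to 10% wider than under infinite-df pooling. No change to design, data collection or the choice of imputation is needed.

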8.0 Study Endpoints*

We will examine within-person changes in blood levels of estradiol, testosterone, dehydroepiandrosterone sulfate (DHEAS), and sex hormone-binding globulin (SHBG) after three weeks of one serving of white wine daily compared to levels after three weeks of one serving of white grape juice daily.

At visits 1, 2, 3, and 4, the BIDMC Clinical Research Center (CRC) nurses will obtain a fasting blood sample. Within 72 hours, Quest Diagnostics will measure hepatic function, a complete blood count, and following visits 2 and 4, they will conduct a lipid panel. On our weekly phone check-ins, we will ask about recent health events such as unscheduled hospitalizations or any symptoms that have developed since the last meeting.

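### Free estradiol, the named primary endpoint, is missing from the endpoint section and from the modelled outcomes, so the plan gives it no model, scale or interval

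*Combined protocol and SAP*

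**What the plan says.** The primary endpoint is named once, at the start of the power text in section 11.0: "Our primary endpoint is free estradiol (estradiol divided by SHBG".

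Section 8.0, which is the endpoint section, says: "We will examine within-person changes in blood levels of estradiol, testosterone, dehydroepiandrosterone sulfate (DHEAS), and sex hormone-binding globulin (SHBG". The comparison is between the end of three weeks of wine and the end of three weeks of juice. It does not mention the ratio, and it does not mark any hormone as primary.

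The analysis paragraph of section 11.0 repeats those four outcomes: "We will construct linear mixed models to examine within-person changes in levels of estradiol, testosterone, DHEAS, and SHBG from grape juice to white wine". Each model has a random intercept per woman, with treatment and sequence as its fixed terms. On scale the paragraph says: "We will use a logarithmic transformation for skewed distributions of the sex hormone levels". On the analysis population it says "Our primary analysis will use an intention-to-treat (ITT) approach", without saying which outcome that primary analysis concerns.

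The power figures are given "as shown below at a two-sided 0.05 significance level" and cover estrone sulfate and DHEAS only. The plan has no multiplicity rule.

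**The concern.** A reader who follows section 8.0 and the model paragraph would fit four models, and none of them has the declared primary endpoint as its outcome. The sentence in the power text gives a formula for free estradiol but no model, scale or interval.

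The gap would be harmless if the four models settled the matter, but they do not. Section 2.0 reports that alcohol raises both estrogen and SHBG, which are the numerator and the denominator of the ratio. Estradiol alone and estradiol divided by SHBG can therefore give different answers, and the plan's sections point to different ones.

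The hypothesis in section 1.0 is that the usual rise will not be seen on aromatase inhibitor therapy. A conclusion of that kind depends on how far an interval excludes an increase. Section 11.0 discusses excluding increases only for DHEAS and plans no interval for the primary endpoint.

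**Working it through.** **1. Where the ratio appears**

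| Place | Hormone quantities named | Ratio? |
|---|---|---|
| 8.0 Study Endpoints | estradiol, testosterone, DHEAS, SHBG | no |
| 9.0 visit schedule | estradiol and estrone, SHBG, DHEAS, testosterone | no |
| 11.0 mixed models | estradiol, testosterone, DHEAS, SHBG | no |
| 11.0 power text, first sentence | free estradiol = estradiol/SHBG | yes, called primary |
| 11.0 power table | estrone sulfate, DHEAS | no |
| 11.0 laboratory text | estradiol, estrone, testosterone, SHBG, DHEAS | no |

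The schedule has both components measured at visits 1 to 4, so the ratio can be computed. What is missing is its specification.

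**2. The plan's own power figures**

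Inputs from section 11.0 are SDs of within-person differences of 42% (estrone sulfate) and 13% (DHEAS) and a two-sided 0.05 level. Section 23.0 gives 20 completers. Solving the noncentral t with 18 degrees of freedom gives a minimum detectable difference of k × SD/√20, with k = 2.071, 2.962 and 3.430 at 50%, 80% and 90% power.

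- Estrone sulfate: 42/√20 = 9.391, giving 19.45, 27.82 and 32.21% (stated 19, 28, 32).
- DHEAS: 13/√20 = 2.907, giving 6.02, 8.61 and 9.97% (stated 6, 9, 10).

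All six figures reproduce. The table is sound, but it does not concern the primary endpoint. The documents give no SD for free estradiol. If that SD were 13, 30, 42 or 60% (assumed range), the 80% figure would be 2.962 × SD/√20 = 8.6, 19.9, 27.8 or 39.7%.

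**3. Whether the four models imply the answer for the ratio**

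*Point estimate.* On the log scale, effect on log(estradiol/SHBG) = effect on log estradiol − effect on log SHBG, provided both are logged and the same records enter both models. If, for illustration, both rise by 10%, the ratio changes by 1.10/1.10 = 1.00. Estradiol has risen and the primary endpoint has not moved.

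*Standard error.* SD(log ratio) = √(s₁² + s₂² − 2ρs₁s₂), where ρ is the correlation between the two within-person differences. Separate models do not estimate ρ. With s₁ = s₂ = 0.30 (assumed):

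- ρ = −0.5: √0.27 = 0.52
- ρ = 0: √0.18 = 0.42
- ρ = 0.5: √0.09 = 0.30

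The interval's width therefore varies by a factor of 0.52/0.30 ≈ 1.7 over this range.

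*Scale.* Logging is conditional on skewness, so even the point-estimate identity is not guaranteed.

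**4. Error rate if the primary designation were disregarded**

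Suppose wine has no effect and four tests are run at two-sided 5%.

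| Correlation (assumed) | At least one p<0.05 | At least one significant increase |
|---|---|---|
| independent | 1 − 0.95⁴ = 18.5% | 1 − 0.975⁴ = 9.6% |
| 0.3 (simulated) | 17.4% | 8.7% |
| 0.5 (simulated) | about 16% | 7.8% |
| single test | 5% | 2.5% |

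**The case against.** The strongest reply is that the plan does name one primary endpoint, in the singular, with a formula, and in the same section as the models. The listed hormones are by implication not primary, and a team that presented a lone DHEAS result as the trial's answer would contradict its own protocol. This stands.

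It rules out a stronger reading that a reader might infer, namely that the trial has four co-equal endpoints and a false-positive rate of 18.5%. That figure holds only if the power-text sentence is ignored. It also counts falls as well as rises, and the question is about increases, for which the figure is 9.6%. Nor do the documents give free estradiol an explicit error-control role.

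A second reply is that the natural reading applies the same mixed model to the ratio, since both components are assayed and modelled. This stands in part. No data are lost, and on the log scale the point estimate could be inferred. The interval could not be, and the scale is left open.

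A third reply is that this is a 20-woman pilot, and section 11.0 says power is only one dimension of its merit. That limits how serious the gap is, but pilot status does not settle which quantity carries the conclusion.

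**Conclusion.** The point holds as an inconsistency between sections. The declared primary endpoint is absent from the endpoint section and from the modelled outcomes, and it has no stated model, scale, interval or power. It can change the conclusion because estradiol and the ratio may diverge, which follows from section 2.0's statement that alcohol raises both estrogen and SHBG. How far they would diverge on aromatase inhibitor therapy cannot be computed from the documents.

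The 18.5% (9.6% for false increases) is a worst case that assumes independent tests and a disregarded primary endpoint. It is not the plan's stated error rate. The SDs and correlations used for the ratio are assumptions.

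The gap should be closed, but it does not threaten data collection. Sections 9.0 and 10.0 hold the hormone samples until all participants finish, so the hierarchy can still be fixed without knowledge of results if those assays have not been run.

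**What to change.** - **Section 8.0:** name free estradiol, end of wine versus end of juice, as the single primary endpoint. List estradiol, testosterone, DHEAS, SHBG and estrone as secondary. Estrone is in the visit schedule and the laboratory text but is not modelled.
- **Section 11.0, models:** add log(estradiol/SHBG) as the first outcome, whether or not the components look skewed. Report the back-transformed wine-to-juice ratio with a 95% CI. State that the primary analysis refers to this outcome and that the main conclusion rests on its estimate and interval.
- **Section 11.0, power:** state that the table covers estrone sulfate and DHEAS and not the primary endpoint. Either give an SD for free estradiol with its source, or say that none is available and that the pilot will supply it.

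The cost is a few sentences, with no new samples, assays or visits. There are two real downsides. A lone significant secondary hormone can no longer carry the conclusion, and the plan must acknowledge that its primary endpoint has no stated power.

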2.0 Background*

Several controlled feeding studies among premenopausal and postmenopausal women showed that alcohol supplementation for a few weeks acutely increases estrogen and sex hormone-binding globulin (SHBG) levels. However, data on how light intake of alcohol impacts sex hormone levels among women receiving estrogen suppressants is critical for guiding postmenopausal women with estrogen receptor-positive (ER+) breast cancer about the safety of alcohol intake.

In a cross-sectional study of 490 postmenopausal breast cancer survivors (Wayne S. *Cancer Epidemiol Biomarkers Prev.* 2008;17(11):3224-3232.), alcohol intake and sex hormone levels were strongly associated despite the relatively low range of alcohol intake in study participants. Tamoxifen use dampened the association between alcohol intake and dehydroepiandrosterone sulfate (DHEAS) levels, and among participants with ER+ tumors, there was no association between alcohol intake and sex hormone-binding globulin (SHBG).

Although alcohol intake raises sex hormone levels, it is unknown if that effect persists on aromatase inhibitor therapy, in part because the mechanism underlying alcohol's effect on sex hormone levels is not well understood. Despite the potential

risks of alcohol intake on hormone levels, a cancer diagnosis is not associated with long-term changes in daily alcohol intake. Furthermore, there have been discrepant findings on the association between alcohol intake and breast cancer recurrence and survival. Some studies have found that alcohol intake is not associated with a higher rate of breast cancer mortality, and it may even lower the rate of all-cause mortality.

There have been no studies to examine alcohol's effect on sex hormone levels among postmenopausal women with estrogen receptor-positive (ER+) breast cancer receiving aromatase inhibitor therapy. This information is needed for them to make informed decisions about their alcohol intake and its potential effect on adjuvant aromatase inhibitor therapy. Therefore, we will conduct a pilot randomized controlled crossover trial to assess whether alcohol at low "real-world" levels of intake increases sex hormone levels in the presence of aromatase inhibitor therapy.

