Study Day	0	1-7	8-14	15	15-21	22-28	29-35	36	36-42	43-49	50	51-57	58-64	65-71	72		
Window Allowance (Days)		±4	±4	±4	±4	±4	±4	±4	±4	±4	±4	±4	±4	±4	±4		
Type of Visit	Clinic	Phone	Phone	Clinic	Phone	Phone	Phone	Clinic	Phone	Phone	Clinic	Phone	Phone	Phone	Clinic		
Payment					\$20				\$30			\$30				\$50	
Admin, Body Measurements, and Vitals																	
Consent, contact information		X															1
Eligibility: e.g., Alcohol use Disorders Identification Test (AUDIT) and hepatic panel if none in the past 12 months*		X															1
Randomization			X														1
Verification of consent and documentation			X						X		X				X		4
Height			X														1
Weight, waist circumference			X						X		X				X		4
Vital signs- blood pressure, heart rate			X						X		X				X		4
Distribute drink			X								X						2
Measure leftover drink									X						X		2
Pay participant, reimburse parking			X						X		X				X		4
Blood Draw																	
Hepatic panel	*		X						X		X				X		4
Complete blood count with differential			X						X		X				X		4
Basic metabolic panel (fasting)			X														1
Lipid panel										X					X		2
Estradiol and estrone			X						X		X				X		4
Sex hormone binding globulin (SHBG)			X						X		X				X		4
Dehydroepiandrosterone sulfate (DHEAS)			X						X		X				X		4
Testosterone			X						X		X				X		4
Weekly Call																	
Health events		X	X		X	X	X		X	X	X	X	X	X	X		10
Other health changes		X	X		X	X	X		X	X	X	X	X	X	X		10
Alcohol and grape juice timeline follow-back		X	X		X	X	X		X	X	X	X	X	X	X		10
Weekly REDCap Questionnaires																	
Pittsburgh Sleep Quality Index (PSQI)									X						X		2
Depressive Symptoms (CES-D-10)		X	X		X	X	X		X	X	X	X	X	X	X		10
Overall pain (visual analog scale)		X	X		X	X	X		X	X	X	X	X	X	X		10
Open text-any questions, concerns, comments		X	X		X	X	X		X	X	X	X	X	X	X		10

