We will obtain laboratory results about the safety measures from the Quest eResults system and manually enter the data into the study database. We will retain paper copies of the reports and periodically conduct audits to compare the entered data with the paper copies to ensure that it was accurately entered in the study database.

The Brigham Research Assay Core (BRAC) will conduct specimen analyses for sex hormones. We will centrifuge the samples for sex hormone assays and freeze the serum in aliquots at -80°C. At the end of the study, we will bring the samples to the BRAC. They will use liquid chromatography–mass spectrometry to measure estradiol, estrone, and testosterone, and they will use chemiluminescence to measure sex hormone binding globulin (SHBG) and dehydroepiandrosterone sulfate (DHEAS). We will follow their sampling, storage, and transport procedures.

We will obtain laboratory results about the sex hormone measures from the Freezerworks database on the BRAC web portal system and manually enter the data into the study database. We will retain paper copies of the reports and periodically conduct audits to compare the entered data with the paper copies to ensure that it was accurately entered in the study database.

Only members of the research team, including the CRC nurses, will have access to the data and specimens. Quest Diagnostics will transmit results through their secure

eResults system with study-specific account access. We will download results and enter the data into our study-specific REDCap database.

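### The primary endpoint is named free estradiol but is calculated as estradiol/SHBG, an index that over-weights SHBG and can hide a rise in free estradiol

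*Combined protocol and SAP*

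**What the plan says.** Section 11.0 of the combined protocol and SAP, in its power paragraph, reads "Our primary endpoint is free estradiol (estradiol divided by SHBG". It gives no binding equation, albumin term, binding constants or direct free-hormone assay.

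The mixed models described earlier in Section 11.0 address "within-person changes in levels of estradiol, testosterone, DHEAS, and SHBG from grape juice to white wine", with a log transformation where distributions are skewed. Neither that list nor the one in Section 8.0 contains free estradiol or the ratio.

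On measurement, Section 11.0 says of the assay laboratory: "They will use liquid chromatography–mass spectrometry to measure estradiol, estrone, and testosterone". SHBG is measured by chemiluminescence. The assessment table in Section 9.0 schedules estradiol, SHBG, testosterone and a "hepatic panel" at all four study visits.

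Two further statements matter. Section 2.0 reports from controlled feeding studies that a few weeks of alcohol raises both estrogen and SHBG. Section 1.0 hypothesises that the usual increases in sex hormones will not be seen in women on an aromatase inhibitor.

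**The concern.** Dividing by SHBG tracks free estradiol only if practically all estradiol in blood is bound to SHBG. If some is unbound or bound elsewhere, for example to albumin, the free concentration moves less than inversely with SHBG. The quotient then over-corrects.

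The direction matters in this trial. The plan's background expects alcohol to raise SHBG as well as estrogen. A rise in SHBG pushes the ratio down further than it pushes free estradiol down, so a genuine rise in free estradiol can appear as no change. No change is what the trial hypothesises, and Section 1.0 says the result is meant to inform women's decisions about drinking. False reassurance is the costly error.

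**Working it through.** **The plan's own figures.** The only design figures are the minimum detectable differences in Section 11.0, "at a two-sided 0.05 significance level". Their inputs are "we estimate the SD of within-person differences to be 42% for estrone sulfate and 13% for DHEAS" and, from Section 23.0, 20 completers. A paired comparison with noncentral t on 19 degrees of freedom and SE = SD/√20 gives, at 50/80/90% power:
- estrone sulfate: 19.4/27.7/32.1% (plan: 19/28/32%)
- DHEAS: 6.0/8.6/9.9% (plan: 6/9/10%)

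The table reproduces to rounding. It covers neither the ratio, SHBG nor free estradiol, so the size of the present problem has to be derived.

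**Model.** At binding equilibrium, free E2 = E2 / (1 + K_S × SHBG + K_A × albumin). Let s be the baseline share of estradiol bound to SHBG, s = K_S × SHBG / (1 + K_S × SHBG + K_A × albumin). This simple form takes available SHBG sites as proportional to total SHBG and ignores competition from testosterone. If SHBG changes by a proportion c and estradiol is fixed:
- free estradiol is multiplied by 1/(1 - s + s(1 + c)) = 1/(1 + sc)
- the ratio is multiplied by 1/(1 + c)

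The two agree only at s = 1 or c = 0. On the log scale the ratio gives SHBG a weight of -1, while free estradiol gives it about -s. The over-weighting is thus about 1/s for small changes and always exceeds 1 when s is below 1.

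**Inputs.** The documents give neither s nor any size for an SHBG change. I assume s = 0.3 to 0.6 and c = ±10% and ±20%.

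**Results, estradiol unchanged**

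| SHBG change | Ratio | Free, s = 0.3 | Free, s = 0.6 | Ratio ÷ free | Excess, points |
|---|---|---|---|---|---|
| +10% | 1/1.1: -9.1% | 1/1.03: -2.9% | 1/1.06: -5.7% | 3.1 to 1.6 | 6.2 to 3.4 |
| +20% | 1/1.2: -16.7% | 1/1.06: -5.7% | 1/1.12: -10.7% | 2.9 to 1.6 | 11.0 to 6.0 |
| -10% | 1/0.9: +11.1% | 1/0.97: +3.1% | 1/0.94: +6.4% | 3.6 to 1.7 | 8.0 to 4.7 |
| -20% | 1/0.8: +25.0% | 1/0.94: +6.4% | 1/0.88: +13.6% | 3.9 to 1.8 | 18.6 to 11.4 |

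**Results, estradiol and SHBG both up 10%** (the direction in Section 2.0)
- ratio: 1.1/1.1 = 1.000, a change of 0.0%
- free estradiol, s = 0.3: 1.1/1.03 = 1.068, +6.8%
- free estradiol, s = 0.6: 1.1/1.06 = 1.038, +3.8%

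**Sensitivity to s.** With s from 0.2 to 0.8 and a 10% SHBG change in either direction, ratio ÷ free runs from about 5.4 down to 1.2. A wider set of assumptions (K_S 0.3 to 0.7 × 10⁹ L/mol, K_A 4 to 6 × 10⁴ L/mol, albumin 43 g/L, SHBG 20 to 120 nmol/L) gives 1/s from 1.3 to 7.4. The multiple depends on these choices. The direction of the over-weighting does not.

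**The case against.** **The formula is printed.** The endpoint is defined and reproducible, so this could be called a labelling point. That stands in part: the ratio is a valid index of itself. But an estimate and interval reported as free estradiol will be read as describing free hormone, and for that quantity they are mis-scaled.

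**Estradiol and SHBG are also modelled separately.** An SHBG-driven result would therefore be visible. This is a real mitigation, but it does not correct the primary estimate.

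**SHBG may not move.** Section 2.0 says of its cross-sectional study of survivors that "among participants with ER+ tumors, there was no association between alcohol intake and sex hormone-binding globulin (SHBG". If that held within women here, the ratio and free estradiol would change by the same percentage and there would be no error. The same section reports SHBG rises in controlled feeding studies, so the plan cannot rely on it.

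**Stronger readings that the documents do not support:**
- A reader might infer a fixed multiple for any SHBG change. The multiple rests wholly on s, which the documents do not give.
- A reader might call the change in the ratio spurious. With estradiol fixed and SHBG falling, free estradiol does rise; the ratio exaggerates that rise and does not invent it.
- A reader might think SHBG can be mis-weighted in either direction. It is always over-weighted; only the sign of the error follows the SHBG change.
- A reader might set the movement of the ratio against the 7-22% increases quoted in Section 11.0. Those are for estrone sulfate, and the error is the excess over the true change: 3.4 to 8.0 points for a 10% SHBG change, mostly below or at the lower end of that range. Only the larger assumed shifts fall well inside it.
- A reader might expect a falsely high result on wine. That needs SHBG to fall on wine relative to juice, which no section suggests.

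**The remedy imports outside constants.** True, and the documents do not name albumin as an analyte. Hence the sensitivity analysis and the minimum option under the fix.

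**Conclusion.** The point holds. Estradiol divided by SHBG is an index, and calling it free estradiol over-weights SHBG whenever less than all estradiol is bound to SHBG and SHBG changes within a woman. Under the assumed s of 0.3 to 0.6, the over-weighting is about 1.6- to 3.9-fold for SHBG changes of 10% to 20%; other values of s widen that range. The most relevant case is the one the plan's background anticipates: with both analytes up 10%, the primary endpoint shows 0.0% while free estradiol is up about 3.8% to 6.8%. Analysed as written, the trial could miss a rise and appear to support its hypothesis of no increase.

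The conclusion that the ratio over-weights SHBG needs only that some estradiol is unbound or bound elsewhere. The sizes rest on the assumed s, the assumed SHBG changes and the simple binding model. This should be changed before the hormone data are analysed. It does not make the endpoint undefined or the separate hormone analyses unsound.

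**What to change.** In Section 11.0, define primary free estradiol by a pre-specified mass-action calculation from same-visit estradiol, SHBG, testosterone and albumin. Name the binding constants in advance and add a sensitivity analysis across them. First confirm whether the hepatic panel reports albumin; if it does not, use one stated fixed value. Keep estradiol/SHBG as a secondary result labelled an index, and report it beside the separate changes in estradiol and SHBG.

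At minimum, rename the endpoint the estradiol/SHBG ratio and state that no conclusion about free estradiol will be drawn from it alone.

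The cost is SAP wording and a few lines of code. The hormones and the panel are already scheduled at all four visits, so no further blood draw is needed. The drawbacks are reliance on external binding constants and the need to carry albumin from the safety results into the analysis file.
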